Psoriatic arthritis (PsA) is a heterogeneous autoimmune disease that occurs in one in three people with the skin disease psoriasis. PsA can cause arthritis (joint inflammation), enthesitis (tendon and ligament inflammation), sausage digits (swollen entire finger or toe), spondyloarthritis (spinal inflammation). Skin involvement by psoriasis is also highly variable in terms of psoriasis type and location. Through combined skin and musculoskeletal involvement, psoriatic disease has a significant life impact with decrease quality of life including uncomfortable symptoms, ability to participate in life and functioning. Medications used to treat PsA have sometimes an uneven effect on the various PsA manifestations where some are more effective for skin while others more effective for the joints. In this context, clinical care and treatment of PsA is a complex process which balances disease activity with medication risks and benefits as well as patient priorities. Professional PsA treatments guidelines state that PsA treatment goals are disease remission or low disease activity. Several studies to date have shown that physicians tend to overestimate remission and low disease activity in PsA patients when compared to disease activity indices. Also patients and physicians frequently do not align on perceptions of remission or low disease activity. In the proposed study we aim to identify predictors of successful treatment from a patient perspective on a range of disease measures including psoriasis, arthritis, enthesitis, dactylitis, patient reported outcomes, and laboratory assessments which are routinely collected in the clinical care of PsA. Secondary endpoints are to quantify longitudinally how stable a state of treatment success is from a patient perspective, and to define score ranges for disease measurements, including health-related quality of life measures, that correspond to treatment success from a patient perspective. **The impact of this research is that we will be able to define parameters predictive of achieving treatment success from a patient perspective, which will then inform goals of care for psoriatic arthritis.**

2. Objectives

Primary objective

To determine predictors of reaching PsA treatment goals/treatment success (primary outcome) from a patient perspective in an academic PsA guideline-based treatment cohort. Conversely, to determine adverse predictors to reaching this desirable state. The primary outcome determination is based on the patients' report of whether they are/are not at goal with their PsA treatment.

Secondary objective(s)

To estimate the following parameters:

- A. Prevalence of patients reporting they met PsA treatment goals (successful treatment) from their perspective.

- B. Frequency and direction of longitudinal transitions between treatment goals/met not met states: 3 observations/participant.
- C. Score ranges that correspond to a status of patients' treatment goals met on a set of PsA outcome measures used in the study, including composite disease activity measures.
- D. On the same set of PsA outcome measures, meaningful change values in patients who transition longitudinally to the better and worse categories.

3. Background

Efficacy of therapeutics in PsA is incomplete, considering at most 60% of patients achieve the primary efficacy outcome in clinical trials. More so, treatment goals from the patient perspective, as well as alignment of patient opinion with index-based definitions of treatment success are part of the knowledge gap in PsA. In clinical practice, desirable treatment targets have been defined by experts as Disease Activity in Psoriatic Arthritis (DAPSA) low disease activity or remission, or Minimal Disease Activity (MDA)2. The clinical DAPSA score is computed by adding the sum of tender (out of 68) and swollen (out of 66) joints with patient global assessment and patient reported pain (each on a scale of 0-10). DAPSA remission state is defined by a score≤ 4, and DAPSA low disease activity as ≤ 14. MDA is a checklist based state defined as achieving five out of the following seven criteria: ≤ 1 swollen joint, ≤ 1 tender joint, ≤ 1 tender enthesal point, HAQ-DI score ≤ 0.5 (range 0-3), patient reported pain ≤ 1.5, patient global assessment ≤ 2, body surface area psoriasis ≤ 3%. It is of great interest to ascertain if guideline-based PsA clinical care achieves individual patient goals as articulated by patients, and to identify predictors of achieving individual patient goals from PsA treatment.

4. Study Procedures

All study assessments will be programmed in the electronic medical record (Epic EMR) with the help of the epic physician builder who is co-investigator on the study ([name] [name], MD). Demographics, key comorbidities (cardiovascular disease, hypertension, diabetes, obesity, osteoporosis, thromboembolic disease, cancer), routine laboratories including inflammatory markers, and disease characteristics will be updated **at every visit**. Information that does not change such as disease onset for psoriasis and psoriatic arthritis will be recorded only at baseline. Study visits will occur at 3-4 month intervals in conjunction with clinical care. Disease assessments will comprise physician assessments (Table 1 a,b), laboratories (Table 2), and patient reported outcomes (Table 3 a,b). Medication doses and changes in medications will be recorded longitudinally. Disease activity measures will be programmed in the medical record such that scores are automatically generated from the primary data elements as illustrated in Table 4.

Table 1a. Physician assessments

PsA Phenotype smartform	Elements
CASPAR classification criteria (cumulative)	Psoriasis (active, history, family history), Nail psoriasis, Dactylitis, Negative rheumatoid factor, Juxtaarticular new bone (radiographic PsA)
Extraarticular manifestations (cumulative)	Uveitis, Inflammatory bowel disease, Inflammatory back pain, Psoriasis type (plaque, pustular, inverse, guttate, erythrodermic) and special locations (scalp, palmoplantar, intergluteal cleft/perianal), Elevated CRP
Comorbidities (from problem list)	Cancer of skin (not melanoma), Melanoma skin cancer, Cancer other than skin (fill in), Coronary artery disease, Diabetes, Fatty liver disease, Obesity , Osteoporosis, Stroke, Thyroid disease, Vitiligo

Table 1b. Disease activity measures

Psoriatic arthritis areas/domains	Physician assessments
Musculoskeletal Arthritis	Tender/swollen joint counts 66/68
Dactylitis	Dactylitis index (LDI basic) (0-20)
Enthesitis	Enthesitis index (SPARCC) (0-18)
Spondyloarthritis	Antropometrics (Cervical range of motion anteroposterior and lateral: occiput to wall, degrees lateral rotation; Thoracic expansion; Lumbar spine: Schober 10 and 15 cm, Lateral lumbar flexion)*
Skin and nails	Psoriasis body surface area affected (BSA%); Psoriasis location (scalp, upper extremities, lower extremities, torso, abdomen); Psoriasis phenotype (plaque, pustular, inverse, guttate, erythrodermic) Investigator global assessment (0-4); Nail disease (pitting, onycholysis, and surface area affected)

* assessed only at baseline

Table 2. Laboratory assessments

Psoriatic arthritis areas/domains	Laboratory test
Inflammatory markers	C reactive protein (CRP, mg/dL), ESR

We will also assess complete blood counts and comprehensive metabolic panel at every visit as part of usual clinical care. We will retrospectively abstract serologic information collected as part of usual clinical care from the medical record (rheumatoid factor, anti-cyclic citrullinated peptide (anti-CCP) status, HLA-B27, and ANA).

Table 3a. Patient reported treatment success impression

The final questions will be refined with patient research partners to make sure these are formulated such that patients understand we are assessing at each visit whether they have achieved their personal treatment goals for their psoriatic arthritis.

Patient impression of PsA treatment goals met	Response options
1. "Today, considering the level of control of your psoriatic arthritis and psoriasis, do you consider your treatment has been successful?"	1. yes 2. no
2. "If in your opinion, psoriatic arthritis and psoriasis treatments have NOT been successful for you, please choose the three most important manifestations and life impact aspects that are still active for you (from your psoriatic arthritis and psoriasis)."	1. inflamed joints, 2. inflamed tendons, 3. back/spine inflammation, 4. skin psoriasis, 5. nail psoriasis, 6. scalp psoriasis, 7. Pain, 8. Fatigue, 9. Stiffness, 10. Ability to be physically active/exercise, 11. Ability to participate with family activities, 12. Ability to work, 13. Ability to participate in social activities, 14. Emotional impact, 15. Ability to be independent in my daily activities, 16. Other, please fill in.

Patient impression of PsA treatment goals met	Response options
3. Patient acceptable symptom state: "If you were to remain for the next few months as you were during the past week, would this be acceptable or unacceptable for you?"	1. acceptable 2. unacceptable

Table 3b. Patient reported outcomes for disease status and life impact

Psoriatic arthritis areas/domains	Patient reported outcomes
Musculoskeletal	Bath Ankylosing Spondylitis Disease Activity Index (BASDAI)
Health related quality of life	Psoriatic Arthritis Impact of Disease (PsAID12, PsA specific) PROMIS Profile 29 (generic)
Pain	Pain visual analog scale (VAS, 0-100 mm) PROMIS Pain interference (Profile 29)
Physical function	PROMIS Physical Function 10
PsA patient globals	Patient global Arthritis (GRAPPA) (VAS, 0-100 mm) Patient global Psoriasis (GRAPPA) (VAS, 0-100 mm)
Fatigue	PROMIS Fatigue 8a
Participation, Depression, Anxiety Sleep quality	PROMIS Profile 29

Table 4. Disease activity measures (programmed in EMR and calculated automatically from elementary data)

Disease activity measure	Components and calculation
Disease Activity Psoriatic Arthritis (DAPSA) Cutoffs Remission \leq 4 Low $4 \leq 14$ Moderate $14 \leq 28$ High ≥ 28	Tender/swollen joint counts: 68/66 Patient global (0-10) Patient pain (0-10) C reactive protein (mg/dL) DAPSA = 68tender joints + 66swollen joints + patient global + pain + CRP (ranges from 0 to more than 154) Clinical DAPSA = 68tender joints + 66swollen joints + patient global + pain (0-154)
Very low disease activity (VLDA) and Minimal disease activity (MDA) VLDA (7/7 criteria met) MDA (5/7 criteria met)	Set of 7 criteria: 1. Tender joint count $68 \leq 1$ 2. Swollen joint count $66 \leq 1$ 3. Patient global $\leq 2/10$ 4. Pain $\leq 1.5/10$ 5. Health assessment questionnaire disability index ≤ 0.5 6. Enthesitis ≤ 1 7 Body surface area psoriasis $\leq 3\%$

Patients will be enrolled in CRMS and the CRMS study flag in Epic will be used to identify patients for research visits and data extraction. The unique study identifier will be linked to the patients' JHH medical record number and only study staff will have access to the key table. This will allow study staff to keep track of enrollment and study visits and to specify data query parameters to the EPIC team at the stage of data extraction. If the patient signs consent and has a study visit on the same day, the CRMS flag will not be available to trigger specific Epic content, since the update from CRMS to EPIC takes about 24 hours. Because of this, we will institute a patient-level Smartdata element in Epic that will be flagged after the patient signs consent. This will also indicate inclusion in the study and can be used to trigger specific Epic content for the visit.

Safety assessments: All adverse events (AE) will be recorded and managed per usual clinical care. Serious adverse events (SAE) are defined as adverse events that meet any of the following criteria: result in death; are life-threatening (i.e., in the opinion of the Investigator(s) the subject is at immediate risk of death from the AE); require inpatient hospitalization or prolongation of existing hospitalization; result in persistent or significant disability/incapacity (a substantial disruption of the subject's ability to conduct normal life functions); represent a congenital anomaly/birth defect; constitute an important medical event. As part of usual clinical care, some patients participating in the study will be taking apremilast. Any SAE due to apremilast must be reported immediately (i.e., within 24 hours of the Investigators' knowledge of the event) to Amgen Inc Safety by facsimile. A written report (prepared by the Investigator(s) using an SAE Report Form or a 3500A Medwatch form is to be faxed to Safety (see below for contact information).

Amgen Inc Drug Safety Contact Information:

Amgen Inc Corporation
Global Drug Safety and Risk Management
[name]
[name]
[contact]
E-mail: [contact]

Pregnancies: Pregnancies and suspected pregnancies (including a positive pregnancy test regardless of age or disease state) of a female subject or the female partner of a male subject occurring while the subject is on apremilast, or within 30 days of the subject's last dose of study drug, are considered immediately reportable events. Apremilast is to be discontinued immediately. The pregnancy, suspected pregnancy, or positive pregnancy test must be reported to Amgen Inc Safety immediately facsimile using the Pregnancy Report form provided by Amgen Inc.

5. Inclusion/Exclusion Criteria

Inclusion criteria: English speaking/reading adults, ages 18 to 95 years who are patients in the Johns Hopkins Arthritis Center and/or the Psoriatic Arthritis Clinical Program (PI, [name] MD MHS directs the PsA program) and are followed every 3-4 months. Participants have to meet CASPAR classification criteria for psoriatic arthritis (supplementary material), and be able to interact with touch screen computer.

[figure not shown]
Exclusion criteria: None

6. Drugs/ Substances/ Devices – Not Applicable

7. Study Statistics

Grouping of treatment goals met or not met is based on the primary outcome at each study visit (Fig1).

Figure 1. Determining patient status in terms of treatment goals met (treatment has been successful from the patient's perspective) or not.

a. Predictors of successful treatment/reaching PsA treatment goals (primary outcome) from a patient perspective: In the longitudinal dataset with up to three visits per participant, we will examine predictors of 'treatment goals met' status using logistic regression with covariates disease characteristics and patient reported variables. We will identify predictors associated with a transition state from unmet to met, a stable status of treatment goals met, as well as predictors of stable status of unmet goals or transition in the negative direction (state variable with 4 categories: unmet to met, stable met, stable unmet, met to unmet). Full visits for this study must be in-person so that the physician assessment of the patient's disease is complete.

b. Prevalence of patients reporting successful treatment/they meet PsA treatment goals from their perspective: We will perform exploratory data analysis to estimate the prevalence of 'patient treatment goals met' status in this longitudinal guideline based therapy cohort. We will then compare characteristics of 'treatment goals met' vs 'not met' patient groups using proportions for binary/categorical (chi square tests) and means for continuous variables (t-tests).

c. Frequency and direction of longitudinal transitions between treatment goals met(successful treatment)/not met states: 3 observations/participant Inperson Visits only: We will determine how patient states change over time to define stability of the notion of successful treatment. Interim Telemedicine visit data will be collected to fill gaps between extended in-person intervals.

d. Score ranges that correspond to a status of patients' treatment goals are met (successful treatment) on a set of PsA outcome measures used in the study, including composite disease activity measures: We will calculate average score ranges for multiple variables of interest that correspond to a status of successful treatment for patients.

e. Meaningful change values in patients who transition longitudinally to the better and worse categories: We will determine change scores in clinical outcomes corresponding to a meaningful change from the patient perspective (MCII). We will determine MCII for various measures using a predictive approach (logistic regression with ROC and AUC). We will perform a similar analysis in patients who go the other direction (from treatment goals met to treatment goals not met).

f. Telemedicine Visits: Data from telemedicine visits will be collected and used to fill gaps in understanding the changes to the patient's health status over time. This is important do to the length of time between In-Person visits due to COVID-19.

8. Risks

September 25, 2020

This study is a longitudinal observational study.

There are no medical risks associated with participating in this research.

There are no additional risks to questionnaire completion. Only the investigators will have access to a list linking personal identifying

information to study number. There are no known financial or legal risks associated with participation in this study.

9. Benefits

There are no direct benefits to participants from participating in the study. It is possible that some patients will benefit from better communicating their disease experience to their own healthcare providers.

Benefits for society include a better understanding of how patients define treatment success, experience and self-manage their disease, and interact with their healthcare providers regarding their disease.

10. Payment and Remuneration

Participants will not receive monetary compensation for their participation. Coupons will be provided to cover the cost of parking at the time of each study visit.

11. Costs

There are no costs associated with participating in this study.

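### The primary item presumes a treatment but no entry or analysis rule requires one, so a 'no' can mean 'not treated' as well as 'treatment not successful'

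*Combined protocol and SAP*

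**What the plan says.** Section 2 defines the outcome by self-report: "The primary outcome determination is based on the patients' report of whether they are/are not at goal with their PsA treatment". Table 3a (Section 4) turns this into item 1, which is about today: "considering the level of control of your psoriatic arthritis and psoriasis, do you consider your treatment has been successful". The only responses are yes and no: "do you consider your treatment has been successful?' 1. yes 2. no". The wording is not final: "The final questions will be refined with patient research partners to make sure these are formulated such that patients understand" that their personal goals are being assessed.

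Section 5 admits English-speaking adults aged 18 to 95 who attend the centre or its PsA programme "and are followed every 3-4 months", meet CASPAR and can use a touch screen. It then states "Exclusion criteria: None". Current treatment and time on treatment are not mentioned.

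Section 7 classifies each visit as met or not met from the primary outcome, and 7a builds four transition states from those classes. The covariates named in 7a are features of the disease and patient-reported measures. Section 7b sets out to "estimate the prevalence of 'patient treatment goals met' status in this longitudinal guideline based therapy cohort". On drug exposure, Section 4 says "Medication doses and changes in medications will be recorded longitudinally". No part of Section 7 uses those data.

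**The concern.** A person with no treatment cannot answer a question about whether their treatment has worked, yet the form makes them choose yes or no. If they choose no, they are placed with patients whose treatment has been tried and has not succeeded. These groups differ in what could predict a later yes, and 7a has no named variable to separate them.

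Transitions have the same problem. Section 7c wants to learn how stable perceived success is. A patient who answers no before starting a drug and yes once it works adds an unmet-to-met transition that reflects the start of treatment. Without a treatment flag this looks the same as a patient on unchanged treatment whose opinion shifted. Section 7e uses the same transitions as the anchor for meaningful change, so objective D inherits the mixture.

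**Working it through.** The plan states no sample size, expected prevalence or transition rate, so there is no figure to reproduce. The check has two parts.

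**Text check.**
- Does the item presuppose treatment? Yes. Item 3 in Table 3a (acceptable symptom state) can be answered by an untreated patient; item 1 cannot.
- Does eligibility guarantee a treatment? No. Section 5 sets no such condition. Section 4 allows consent and a study visit on the same day, and no run-in is described.
- Does the analysis separate untreated visits? No. Section 7 groups on the answer, and 7a to 7e name no treatment variable.
- Could it? Largely yes, since medication changes are recorded over time. Start dates before baseline are not stated to be collected.

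**Illustration; every input is assumed.** Let f be the share untreated at the first visit, p the share of the others who answer yes (40% or 60%), and y the share of the untreated who answer yes (0% or 10%).

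- Prevalence = (1 − f)p + fy, so the fall from p is f(p − y).
- Share of the unmet group that is untreated = f(1 − y) / (1 − prevalence).
- For transitions, assume further that 40% of the unmet untreated patients and 15% of the other unmet patients are met at the next visit. Share of unmet-to-met transitions from the untreated = 0.40 f(1 − y) / [0.40 f(1 − y) + 0.15(1 − f)(1 − p)].

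Example with f = 10%, p = 60%, y = 0:
- Prevalence is 0.9 × 0.6 = 54%, a fall of 6 points.
- The unmet share is 0.10 / 0.46 = 22%.
- The transition share is 0.040 / (0.040 + 0.054) = 43%.

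| f | Fall in prevalence (points) | Untreated share of unmet group | Share of unmet-to-met transitions |
|---|---|---|---|
| 5% | 1.5-3 | 7-12% | 17-26% |
| 10% | 3-6 | 14-22% | 31-43% |
| 20% | 6-12 | 27-38% | 50-63% |

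If y = p, prevalence does not move at any f. The transition shares are then 12%, 23% and 40%, and these still depend on the assumed 40% and 15%. The calculation shows that transitions are more exposed than prevalence under these inputs. It does not show that the study has this problem to any given degree.

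**The case against.** Several counter-arguments stand, and they limit the point.

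- A reader might infer that untreated or newly treated patients automatically count as treatment failures and later as unmet to met. They do not. Status follows the answer. A patient with mild disease can say yes, and a transition needs a later yes.
- A reader might infer that the planned prevalence is biased. Objective A asks for the proportion of patients reporting goals met and sets no on-treatment restriction, so an all-visit figure matches it. It would be low only as an estimate of a different quantity, success among the treated.
- A reader might want recent switchers set aside as too early to judge. The item asks about today, and a recent switcher with active disease who says no is correctly not at goal. Switching can also follow from unmet goals, so removing switchers would select on prior outcome and could inflate success.
- Improvement after starting treatment is a real transition. Objective B counts it properly, and 7e needs improvers.
- The setting is a treatment cohort under regular follow-up, so untreated patients may be few. Figure 1, on how status is determined, was not available for this review, and it may contain a branch for them.

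None of this supplies a rule for the untreated patient facing a yes/no item. The cohort label and follow-up interval describe the setting without setting a treatment condition, and the planned refinement of the wording does not mention a further response.

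**Conclusion.** The concern holds in a limited form. The primary item cannot be validly answered by a participant who is not on treatment, the plan admits such participants, and nothing in Section 7 distinguishes them. A 'no' can therefore mix two meanings, and unmet-to-met transitions can mix treatment start or change with fluctuation in perceived success.

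The size cannot be stated. It depends on the share untreated and on how they answer, and the documents give neither. The illustrated prevalence effect runs from nil to 12 points over f of 5-20%. The documents do not support a claim that the study's results will be materially biased, or that recent switchers are misclassified. The point is still worth acting on, because the item is open for revision and most of the data needed are already planned.

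**What to change.** 1. **Item 1.** While it is being refined with patient partners, add a response such as 'not currently on treatment for psoriatic arthritis/psoriasis'. State in advance how it counts in the all-visit prevalence; keeping these visits in the denominator as a separate displayed category is the simplest rule.
2. **Objective A (7b).** Keep the all-visit prevalence. Also report prevalence among visits on treatment, without excluding recent switchers.
3. **Transitions (7c).** From the recorded medication changes, flag each visit pair by treatment status at its first visit and by whether treatment was started or changed at or between the two visits. Report transitions separately by this flag. Covering the whole interval matters, because changes made at or after the first visit would otherwise be missed.
4. **Primary model (7a).** Add treatment status at the first visit as a covariate, and a sensitivity analysis excluding untreated visits.

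The cost is one response option and a few sentences in Section 7. No pre-baseline start dates are needed, only treatment status at each visit and changes since the last. The drawbacks are smaller cells in the stratified transition tables, a slightly smaller denominator for the secondary on-treatment prevalence, and the possibility that a well-controlled untreated patient chooses the new response where they would have answered yes.

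### HAQ-DI is a criterion for MDA and VLDA in Table 4 but is not among the assessments in Tables 1-3; if it is not collected, borderline MDA is undetermined and VLDA can never be confirmed

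*Combined protocol and SAP*

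**What the plan says.** **Definitions.** Section 3 (Background) describes MDA as follows: "MDA is a checklist based state defined as achieving five out of the following seven criteria". One of the seven is "HAQ-DI score ≤ 0.5 (range 0-3". Table 4 repeats this as criterion 5, "Health assessment questionnaire disability index", and applies the same seven criteria to VLDA, which needs all seven. VLDA is defined only in Table 4; Section 3 covers MDA alone.

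**Data collection.** Section 4 states: "Disease assessments will comprise physician assessments (Table 1 a,b), laboratories (Table 2), and patient reported outcomes (Table 3 a,b". HAQ-DI does not appear in Table 1a, 1b, 2, 3a or 3b. The physical function row of Table 3b contains one entry, "PROMIS Physical Function 10". No conversion from a PROMIS score to HAQ-DI is given, and there is no rule for a missing MDA component.

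**Derivation.** Section 4 says that "scores are automatically generated from the primary data elements as illustrated in Table 4", and the heading of Table 4 describes its measures as "calculated automatically from elementary data". Table 4 is therefore a list of derived scores, and its inputs have to come from somewhere else.

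**The concern.** Six of the seven inputs to MDA and VLDA can be traced to a listed assessment, and the seventh cannot. If the visit content is built from Tables 1 to 3, a programmed score will lack one component at every visit. A patient questionnaire that was not given cannot be recovered later from the record.

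MDA has a visible place in this study. Section 3 names it among the expert treatment targets and says that "alignment of patient opinion with index-based definitions of treatment success are part of the knowledge gap in PsA". Secondary objective C and analysis 7d extend to composite disease activity measures, and Table 4 contains only two families of these: DAPSA, and MDA with VLDA. MDA or VLDA could also enter 7b as a group characteristic or 7a as a predictor.

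The visits left undetermined for MDA would be the borderline ones, where HAQ-DI alone decides whether five of seven is reached. An automatic formula that counts an absent criterion as not met would lower MDA prevalence and set VLDA prevalence to zero. One that counts it as met would raise both. In either case the result would not show that this had happened.

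**Working it through.** **Step 1. Trace each Table 4 criterion to a listed source.**

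- Tender joint count: Table 1b.
- Swollen joint count: Table 1b.
- Enthesitis: Table 1b (SPARCC index).
- Psoriasis body surface area: Table 1b.
- Pain: Table 3b (visual analog scale).
- Patient global: Table 3b, which lists two, one for arthritis and one for psoriasis. Table 4 does not say which it uses.
- HAQ-DI: no source in Tables 1a to 3b.

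**Step 2. Apply the Table 4 rules without HAQ-DI.** The plan gives no figure to reproduce here. Let k be the number of the other six criteria that are met, and let h be 1 if HAQ-DI would be met and 0 if not. MDA requires k + h ≥ 5, and VLDA requires k + h = 7. The number of patterns with k met is C(6,k), and the total is 2^6 = 64.

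| k | Patterns | MDA | VLDA |
|---|---|---|---|
| 0 to 3 | 1 + 6 + 15 + 20 = 42 | not met | ruled out |
| 4 | 15 | undetermined (4 or 5 of 7) | ruled out |
| 5 | 6 | met | ruled out |
| 6 | 1 | met | undetermined (6 or 7 of 7) |

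MDA is met in 6 + 1 = 7 patterns, not met in 42 and undetermined in 15. It is thus determined in 49 of 64. VLDA is ruled out in 42 + 15 + 6 = 63, undetermined in 1 and confirmed in none.

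**Step 3. Can the pattern count be turned into a share of visits?** The share of visits with MDA undetermined is P(k = 4). It is also the gap between the upper and lower bounds for MDA prevalence, since P(k ≥ 4) − P(k ≥ 5) = P(k = 4). It depends on how often each criterion is met and on how the criteria are correlated, and the documents give neither.

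To show how far the answer moves, assume six independent criteria with a common probability p, so that P(k = 4) = 15 p⁴(1 − p)²:

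- p = 0.1: 15 × 0.0001 × 0.81 = 0.1%
- p = 0.2: 15 × 0.0016 × 0.64 = 1.5%
- p = 0.5: 15 × 0.0625 × 0.25 = 23.4%
- p = 0.7: 15 × 0.2401 × 0.09 = 32.4%
- p = 0.95: 15 × 0.8145 × 0.0025 = 3.1%

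With unequal probabilities (two criteria at 0.3, four at 0.9, independent) the share is 0.49 × 0.6561 + 0.42 × 0.2916 + 0.09 × 0.0486 = 44.8%. All of these inputs are assumptions. The result runs from near zero to almost half depending on what is assumed, so no single figure or range should be presented as an estimate for this cohort.

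**The case against.** The strongest reply is that this is a listing omission and not a gap in collection. Table 4 stands within Study Procedures, names HAQ-DI as a component and says that its scores are built automatically from existing elements. That presupposes that the element is in the medical record, and visits take place alongside clinical care. This reading is plausible, and the point is worded to allow for it. It does not remove the inconsistency. Where the plan relies on usual-care data it says so, as it does for blood counts, the metabolic panel and serologies; it says nothing of the kind for HAQ-DI.

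A second reply is that the impact is inferred. Section 7 never names MDA or VLDA. The sentence on the knowledge gap is background, and no listed objective or analysis tests agreement between MDA and patient opinion. Score ranges and change scores suit continuous measures such as DAPSA better than a checklist state. All of this stands, and it limits the reach of the point to a secondary use of MDA and VLDA.

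A reader might also infer that HAQ-DI was not collected, or that MDA cannot be computed at all. The documents support neither. They are silent on the first, and on the second MDA is still determined in 49 of 64 patterns.

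**Conclusion.** The inconsistency is certain on the text: Section 3 (for MDA) and Table 4 (for MDA and VLDA) require HAQ-DI, and the assessments that Section 4 lists do not include it. The consequences are conditional. Only if HAQ-DI is not collected does MDA become undetermined at exactly four of the other six criteria, and only then does VLDA become a state that can be excluded but never confirmed. Under that condition the logic is exact and needs no distributional assumption.

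It would be wrong to read 15 of 64 as about 23% of visits. It counts patterns, and patterns are not equally likely. The share of visits affected is unknown.

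The effect is confined to MDA and VLDA where they serve as composite measures (objective C, analysis 7d), as group characteristics or as predictors. The primary yes/no outcome, DAPSA and clinical DAPSA do not use HAQ-DI. The point deserves correction because the remedy is cheap and a questionnaire that was never given cannot be recovered, but it does not threaten the main result. The unspecified patient global is a separate, minor ambiguity.

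**What to change.** 1. Add HAQ-DI to Table 3b at each full study visit. If it is already collected, correct Table 3b to list it.
2. For any visit without HAQ-DI, do not let the programmed score silently count the criterion as met or as not met. Class MDA as undetermined when exactly four of the other six criteria are met, and VLDA as undetermined when all six are met. Every other pattern can be classified as usual. Reporting prevalence twice, with the missing criterion counted as met and then as not met, is one suitable way to present the result.
3. State in Table 4 which of the two collected patient globals enters the calculation.

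**Cost.** If HAQ-DI is already collected, item 1 is a one-line correction. If it is not, the cost is a few minutes of patient time per visit and programming of the form and formula in the electronic record. Items 2 and 3 need a few sentences of text and a matching check of the programmed formula.
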